1.0 Clinical Investigation Plan Overview

This study is designed to test the safety and feasibility of Autologous Muscle Derived Cells (AMDC) as a treatment for fecal incontinence in men and women. AMDC therapy seeks to allow remodeling of the external anal sphincter in patients with fecal incontinence from either defined structural defects to, or a generalized weakening of, the external anal sphincter. This treatment is hypothesized to reduce symptoms of fecal incontinence and improve patient quality of life by strengthening the external anal sphincter muscle. The study will treat a total of 50 patients with 250×10^6 cells each.

The primary objective is to determine the incidence of product- or procedure-related adverse events associated with the use of AMDC. Patients will be followed for 12 months.

All eligible patients consenting to study participation will have skeletal muscle tissue harvested using a needle biopsy during an initial outpatient procedure. The harvested muscle tissue will be placed in a hypothermic medium and transported to the manufacturer for processing in their cell processing facility in Pittsburgh, Pennsylvania, USA. The AMDC will be isolated and expanded in culture over several weeks to the final dose of 250×10^6 cells.

After reaching the desired concentration, the isolated and expanded cell population of AMDC will be quality tested and then cryopreserved and shipped back to the investigating physician. The physician will thaw and dilute the cells with saline. The resulting suspension will be injected into the patient's external anal sphincter in a brief outpatient procedure using a small needle under direct vision. Endoanal ultrasound may be used, at the physician's discretion to visualize the location of the injection needle within the external anal sphincter.

A detailed description of the study flow is illustrated in Appendix A.

2.0 Objectives of the Clinical Investigation

2.1 Primary Objective

The primary objective is to determine the incidence of product- or procedure-related adverse events associated with the use of AMDC within 12 months post-treatment.

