3.5 Description of the Necessary Medical or Surgical Procedures

Medical or surgical procedures used in this study include: skeletal muscle biopsy, cell injection into external anal sphincter, routine venipuncture (for blood-borne pathogen tests), pregnancy test (if applicable for women of childbearing age), and standard procedures for care of fecal incontinent patients, including anoscopy, sigmoidoscopy, digital rectal examination, anorectal manometry, and endoanal ultrasound. Refer to the Instructions for Use section regarding biopsy and injection procedures (Section 3.3.2). A full description of other procedures and schedule of events is contained in Section 6.7.

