5.2 Methods to Minimize Risks

The procedure for proper deployment of the product at the intended site is described in the Summary Description of Procedures and the Instructions for Use (Sections 3.3.1 and 3.3.2). Only qualified physicians experienced in performing anorectal procedures will inject the product. Appropriate patient selection and adherence to and training on the research protocol are necessary to reduce product- and procedure-related risk. Routine venipuncture will be performed by qualified personnel.

Injection of AMDC will occur under direct vision. The presence of bleeding or puncture will be ascertained following injection. In addition, this investigation includes a high level of monitoring. The risks of continued incontinence, infection, and allergic reaction to the injected reagents will be assessed through patient report, a patient fecal incontinence diary that will be kept at various time points throughout the study, and clinical follow-up at 3, 6, and 12 months after treatment. Patients will be contacted by phone 24-48 hours and one month after injection to assess for adverse events.

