- Patient has a compromised immune system due to disease state, chronic corticosteroid use or other immunosuppressive therapy
- Patient has any condition that would preclude treatment due to contraindications and/or warnings of concomitant medications or listed in the experimental product labeling
- Patient is simultaneously participating in another investigational drug or device study or the patient has completed the follow-up phase for the primary endpoint of any previous study less than 30 days prior to the first evaluation in this study
- Patient is unable or unwilling to provide informed consent
- Patient is unable or unwilling to commit to the follow-up procedures
- Patient has a medical condition or disorder that may limit life expectancy < two years or that may cause non-compliance with the protocol (e.g. unable to perform self-evaluations and/or accurately report medical history, incontinence symptoms, and/or data)

At Time of Cell Delivery:

- Patient is febrile (defined as temperature $\geq 38.5^{\circ}\text{C}$)
- Patient has current infection
- Patient has active anal fissure, anal fistula, rectal prolapse (full-thickness), or grade III or IV hemorrhoids

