6.5 Point of Enrollment

Patients who meet the inclusion/exclusion criteria are eligible for entry into the study and will have the study protocol and potential risks and benefits of their participation in the study explained to them by the research coordinator and/or physician(s) as appropriate per institutional policy. Informed consent will be obtained in accordance with ICH GCP and applicable regulations, and each patient who agrees to participate in this study will be required to sign an informed consent document prior to any study procedure. Official enrollment will occur at the time of the biopsy.

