6.7.3 Visit 3 (Day 0): AMDC Injection Procedure

[REDACTED] after the muscle biopsy, patients will return to the clinic for a brief outpatient procedure. Prior to injection, if appropriate, patients will also have a urine sample collected for pregnancy testing. Patients will also have their temperature measured and be assessed for signs of infection and changes in anorectal condition that may affect the "At Time of Cell Delivery" exclusion criteria. After confirming eligibility, the AMDC product will be prepared and injected into the external anal sphincter in accordance with instructions for use (as described in Section 3.3). Post-injection, injection sites will be inspected for the presence of bleeding or excessive trauma.

The medication log will be updated if necessary and adverse events will be recorded and reported as appropriate. Patients will be reminded not to change (to the greatest degree possible) their medication regimen, and other coping mechanisms, related to their fecal incontinence condition. Patients will be given a 28-day diary to report fecal incontinence data. The diary should be completed during the 28 days leading up to, and returned to the site at, the next scheduled visit (3 Month Follow-up Visit).

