6.7.4 Phone Contact (Day 1 to 2): Post-treatment Follow-up

Between 24 and 48 hours after treatment, patients will be contacted by phone to determine if any adverse events have occurred and if the patient has any updates for the medication log.

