APPENDIX D: Definitions

Adverse Event or Adverse Experience

An adverse event (AE) is any untoward medical occurrence in a patient or clinical investigation subject administered a pharmaceutical or biologic product and which does not necessarily have a causal relationship with this treatment. An AE can therefore be any unfavorable and unintended sign (including an abnormal laboratory finding), symptom, or disease temporally associated with the use of a medicinal (investigational) product, whether or not related to the medicinal (investigational) product.

Adverse Drug Reaction

An adverse drug reaction (ADR) is any noxious and unintended response to a medicinal product related to any dose where there is a reasonable possibility of a causal relationship, i.e., the relationship cannot be ruled out.

Unexpected Adverse Drug Reaction

An adverse reaction, the nature and severity of which is not consistent with the applicable product information contained in the Investigators Brochure.

Serious Adverse Event or Serious Adverse Drug Reaction

Any events or drug reactions that, either due to their serious nature or due to the significant, unexpected information they provide, justify expedited reporting. A serious adverse event is defined as any event which meets any of the following criteria:

Death: An event, which results in the death of a patient.

Life Threatening Adverse Event: An event that if untreated, would lead directly to the death of the patient.

Hospitalization: An event that results in an admission to the hospital for any length of time.

Prolongs hospitalization: An event, which occurs while the study patient is hospitalized and prolongs the patient's hospital stay (due to potential disability, danger to life, or the event is terminal).

Causes persistent or significant disability or incapacity: An event that leads to a persistent or permanent disabling condition, congenital anomaly or birth defect.

Severity

Severity is a clinical determination of the intensity of a specific event. The event itself may be of relatively minor clinical significance. Severity is not the same as "serious", which is based on outcome or action criteria associated with events that pose a threat to a patient's life or functioning.

Suspected Unexpected Serious Adverse (Drug) Reaction

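### The primary safety incidence in 2.1 has no explicit start and no population, and on the protocol's own usage it leaves out pre-injection biopsy harm and never-injected patients

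*Combined protocol and SAP*

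**What the plan says.** The primary objective (2.1) is the incidence of "product- or procedure-related adverse events associated with the use of AMDC within 12 months post-treatment". Section 1.0 restates it without the post-treatment limit and adds 12 months of follow-up with no stated anchor. Neither section names the patients to be counted.

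The usage of *treatment* can be read from one phone call described twice. Section 6.7.4 has it as "Between 24 and 48 hours after treatment, patients will be contacted by phone"; section 5.2 has it as "Patients will be contacted by phone 24-48 hours and one month after injection to assess for adverse events". All visits headed as post-treatment follow-up come after Day 0.

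The biopsy comes earlier. Section 6.7.2 places it at Week -8 to -6, section 3.3.1 calls it minor surgery, and section 3.5 puts it first: "Medical or surgical procedures used in this study include: skeletal muscle biopsy, cell injection into external anal sphincter". Section 6.5 adds: "Official enrollment will occur at the time of the biopsy". Section 6.4 then has a further set of exclusions headed "At Time of Cell Delivery", and 6.7.3 makes the injection conditional on them: "After confirming eligibility, the AMDC product will be prepared and injected into the external anal sphincter".

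Appendix D defines an adverse event as one occurring "in a patient or clinical investigation subject administered a pharmaceutical or biologic product", and defines relatedness as relatedness to the AMDC treatment. Adverse events are nevertheless recorded at every time point, including the biopsy visit (Table 6-1, 6.7.2), and all of them, related or not, go on the event form (6.10).

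Section 7.2 lists descriptive summaries only. Section 7.1 has 50 patients enrolled; sections 1.0, 6.1 and 6.6 have 50 treated.

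**The concern.** The trial has one primary endpoint, and it is meant to measure harm from the product and the procedure. Every dose requires two invasive steps, a biopsy and an injection. A window that opens at injection misses early harm from the first step, and a count of injected patients misses anyone harmed by a biopsy who never reached the second.

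If the 12-month phrase is taken as an end date only, the omission may disappear, but then neither the start nor the denominator is fixed. Two analysts could report different primary incidences from the same data. Section 6.9 says the study should inform a larger trial, so a clearly defined harm rate is one of its main products.

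**Working it through.** **1. The plan's own figure.** The sample size of 50 cannot be reproduced: 7.1 gives no rate, precision, error level, power or dropout. What can be checked is whether 50 enrolled and 50 treated agree. Enrollment is at biopsy, so they agree only if every biopsied patient is injected. With an assumed share *a* of biopsied patients not injected:

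| *a* (assumed) | biopsied, if 50 are treated: 50/(1−*a*) | injected, if 50 are enrolled: 50(1−*a*) |
|---|---|---|
| 0% | 50 | 50 |
| 10% | 55.6, so 56 | 45 |
| 20% | 62.5, so 63 | 40 |

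**2. Where the window opens.** Sections 6.7.4 and 5.2 describe the same contact, once counted from treatment and once from injection. So *treatment* is the injection, and *post-treatment* implies a Day 0 start. The biopsy is 6 to 8 weeks earlier. Taking 12 months as 52 weeks, that gap is 6/(6+52) = 10.3% to 8/(8+52) = 13.3% of the time from biopsy to Month 12, and it contains the acute biopsy period. A biopsy-related event with onset after injection would still fall inside the window.

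**3. Who could be enrolled and not injected.** The documents show several routes: failing the cell-delivery exclusions (6.4, 6.7.3), cells not meeting acceptance criteria (3.3.1), an inadequate first sample (6.7.2) and withdrawal (6.8). They do not say how often these occur, or whether a patient who fails the Day 0 check is deferred or never injected.

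**4. Whether another section settles it.** Section 7.2 names no window and no analysis set. The sentence in 9.0 about the population analyzed concerns a centre that stops enrolling. Section 6.10 lists procedure-related as an adjudication category but does not say whether the biopsy counts, and the committee is optional.

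**5. Size of the numerator effect.** With 50 biopsied and all injected, one omitted patient is 1/50 = 2.0 percentage points. Let *p* be the assumed share of patients whose only related event is a biopsy event before Day 0. The expected number omitted is 50*p*, and the chance of omitting at least one is 1 − (1−*p*)^50:

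- *p* = 2%: 1 patient; 63.6%
- *p* = 5%: 2.5 patients; 92.3%
- *p* = 10%: 5 patients; 99.5%

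**6. Effect of a single combined figure.** Assume 5 of 50 injected patients have a related event after injection: 5/50 = 10.0% (exact 95% CI 3.3 to 21.8). Add *b* patients whose only related event is a pre-injection biopsy event, and use all biopsied patients as the denominator:

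- *a* = 10%, *b* = 1: 6/56 = 10.7% (4.0 to 21.9)
- *a* = 10%, *b* = 5: 10/56 = 17.9% (8.9 to 30.4)
- *a* = 20%, *b* = 1: 6/63 = 9.5% (3.6 to 19.6)
- *a* = 5%, *b* = 5: 10/53 = 18.9% (9.4 to 32.0)

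The third line falls below 10.0%: the 13 never-injected patients enlarge the denominator and only one patient joins the numerator. A combined proportion can therefore hide injection harm, which is why the two phases need separate figures. The values of *a*, *b* and *p* and the 5 events are all assumptions.

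**The case against.** The strongest reply is that 2.1 is coherent as written. It concerns events associated with the use of AMDC, a never-injected patient has not received AMDC, and three sections describe 50 treated patients. Injected patients counted from Day 0 is then a legitimate safety population, and choosing another is a preference. Much of this stands: the post-injection incidence is worth having and should be kept. But 2.1 also covers procedure-related events, 3.5 lists the biopsy as a procedure, and no section says the biopsy is excluded.

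A second reply is that if 2.1 sets only an end date, biopsy events can be counted, as the restatement in 1.0 would allow. That is possible, but it leaves the start and denominator unstated.

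A third is that the study is descriptive and small by its own account (6.9), and that the sizes above rest on assumed rates. This stands and limits the severity.

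Three stronger readings are tempting and should not be drawn:

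- *The window has no start at all.* The protocol's usage of *post-treatment* implies Day 0; what is missing is an explicit statement.
- *Biopsy harm goes unrecorded.* Table 6-1, 6.7.2 and 6.10 show that it is collected, and the secondary safety objective in 2.2 has no window.
- *The primary figure is known to be too low.* No biopsy event rate or attrition is given, and a change of denominator can move the figure either way.

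**Conclusion.** The point holds as a gap in the definition of the primary endpoint. On the protocol's own usage, the primary incidence leaves out biopsy-related events before Day 0 and events in enrolled patients who are never injected. The conclusion rests on reading *treatment* as the injection, which the two descriptions of the phone call support.

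The numerical effect cannot be determined from the documents. The only firm figure is 2.0 percentage points per omitted patient when 50 are biopsied and all are injected. Severity is minor to moderate: the reported primary result is affected, but no decision rule is.

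**What to change.** - In 2.1, and in 1.0 to match, state that *procedure* includes both the biopsy and the injection.
- In 7.2, report the primary incidence as two figures, each with a 95% confidence interval: (a) first biopsy to injection or study exit, among all biopsied patients; (b) injection to 12 months, among all injected patients.
- An overall biopsy-to-12-months proportion among all biopsied patients may be added, but should not replace (b).
- Amend Appendix D so that the adverse event and relatedness definitions cover the biopsy.
- Reconcile 50 enrolled (7.1) with 50 treated (1.0, 6.1, 6.6).

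The cost is a protocol amendment, one more table and a relatedness judgement for each early event. The data are already collected, so no visit is added. The reported harm may look less favourable than under the present wording.

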2.2 Secondary Objectives

The secondary objectives are to study the effect of AMDC treatment for fecal incontinence on:

- Changes from baseline in the frequency and nature of incontinent episodes at 3, 6, and 12 months post-treatment as measured by a patient fecal incontinence diary

- Changes from baseline in Wexner incontinence score [1] (copy provided in Appendix B) at 3, 6, and 12 months post-treatment
- Changes from baseline in Fecal Incontinence Quality of Life Scale (FIQL) [2] (copy provided in Appendix C) scores at 3, 6, and 12 months post-treatment
- Changes from baseline in sphincter function as measured by anorectal manometry at 12 months
- Changes from baseline in sphincter morphology as measured by endoanal ultrasound at 12 months
- Safety as measured by adverse events

2.3 Claims and Intended Performance that are to be verified

AMDC treatment is intended to be safe and feasible for the treatment of fecal incontinence.

3.0 Product Description and Intended Use

3.1 Intended Use

AMDC is intended for use in external anal sphincter repair (ASR) for the treatment of fecal incontinence due to a weakened or injured external anal sphincter muscle. The purpose is to increase external sphincter functionality by injecting AMDC into the external sphincter muscle tissue.

3.2 General Product Description

Cook MyoSite will perform cell processing and preparation of cell suspensions for study use in their cell processing facility in Pittsburgh, Pennsylvania, USA.

3.3 Summary Description of Procedures and Instructions for Use

3.3.1 Summary Description of Procedures

Muscle Biopsy

The biopsy procedure will involve minor surgery

Prior to the biopsy, patients that are currently taking any form of anticoagulant medication must stop using the medication as per standard of care for outpatient surgery procedures. Muscle biopsies are obtained

using a percutaneous needle biopsy technique. Ultrasound imaging of the thigh may be used to aid in locating the proper muscle region and depth. The skin is prepared by shaving a small area at the site of the muscle biopsy, if necessary, and cleaning with an antimicrobial skin wash. The biopsy site is anesthetized with a local injection of 1% lidocaine (or other appropriate local anesthetic). A small incision of approximately 5 mm is made in the skin to allow the sterile needle to enter and remove muscle tissue.

Isolation and Expansion of the Study Agent

After receipt at the cell processing center, desirable AMDC will be isolated from the tissue biopsy.

Once the desired cell number has been achieved, quality tests following applicable local regulations assure the cells meet acceptance criteria for sterility, contaminants, cell viability, and functional integrity.

Transportation and Storage of the Study Agent

The study agent must remain frozen and undiluted until ready for use.

Dilution and Preparation for Injection

The 2 mL frozen study agent suspension is thawed and diluted with saline. The entire vial contents should be used for injection.

Cell Injection

The patient may receive local anesthesia at the injection site, as determined after discussion between the patient and physician. Using a small needle, multiple percutaneous injections parallel to the anal canal will be performed to place the patient's own processed cells into the external anal sphincter. Endoanal ultrasound guidance may be used at the physician's discretion to assist with needle localization.

3.3.2 Instructions for Use

The current study Procedure Guidelines, which will be provided to physicians and appropriately designated team members at the time of training, must be followed for step-by-step instructions for performing the following:

- Obtaining the muscle biopsy
- Packaging and shipping the muscle biopsy
- Storing and handling requirements of the final AMDC product
- Resuspending the final AMDC product
- Performing the injection procedure

Muscle Biopsy

- Identify the target biopsy site.
- After cleaning and preparing the target biopsy site, anesthetize the skin and subcutaneous tissue with 1% lidocaine (or other appropriate local anesthetic), avoiding contact with muscle.
- Aseptically open the biopsy procurement supplies and prepare according to instructions.
- Incise the skin and deep fascia with scalpel blade.
- Insert the needle and use according to the manufacturer's instructions. Remove the needle and evacuate the specimen into the biopsy medium vial. Close the wound and cover with an appropriate dressing.

Note: It may be necessary to repeat the sampling procedure from the same location to obtain sufficient muscle tissue.

Dilution and Preparation for Injection

Cell Injection

1. If applicable, prepare the injection site with administration of an appropriate local anesthesia.

2. Attach syringe containing thawed product suspension (as described in the instructions for dilution and injection) to the injection needle.
3. Insert the needle tip into the external anal sphincter and slowly inject the prepared suspension.

4.

5. Ascertain the presence of bleeding or excessive trauma at the injection site.

3.4 Summary of Necessary Training and Experience

Training and experience needed for use of the product includes experience performing anorectal procedures and treatment of fecal incontinence. Study investigators will receive additional training related to the muscle biopsy and AMDC injection procedures as appropriate.

3.5 Description of the Necessary Medical or Surgical Procedures

Medical or surgical procedures used in this study include: skeletal muscle biopsy, cell injection into external anal sphincter, routine venipuncture (for blood-borne pathogen tests), pregnancy test (if applicable for women of childbearing age), and standard procedures for care of fecal incontinent patients, including anoscopy, sigmoidoscopy, digital rectal examination, anorectal manometry, and endoanal ultrasound. Refer to the Instructions for Use section regarding biopsy and injection procedures (Section 3.3.2). A full description of other procedures and schedule of events is contained in Section 6.7.

